### 2.3 Correlative Studies Background

Although checkpoint inhibitory agents have been shown to have clinical activity, there is as yet no predictive biomarker for this class of agent. Blocking PD-L1:PD-1 interactions with nivolumab and CTLA-4 signaling with ipilimumab may release the immune checkpoint blockade, allowing tumor infiltrating lymphocytes (TILs), myeloid-derived suppressor cells (MDSCs), M2 macrophages, and N2 neutrophils to mount an immune response [66, 67]. From the pharmacodynamic perspective, a relationship between extent of mutational load and molecular response of the T-cell receptor in CD8+ TILs should be expected following immune checkpoint therapy in cases that are expressing immune checkpoint molecules (i.e., in cases with a high likelihood that immune checkpoint pathways are preventing an immune response against neo-antigens). The “negative control” is that this should not occur in tumors not utilizing the checkpoints being inhibited by therapy, as evidenced by PD1/CTLA-4 TIL phenotyping.

One of the challenges of developing assays to measure the effects of immunotherapeutic agents

[figure not shown]
is that the target is an immune cell rather than a tumor. It is therefore necessary to measure primary effects on immune cells and secondary effects on the cancer cells, as well as the interactions between these two populations (Figure 6.2). Experimental models with an intact immune system are required for this, thereby excluding immunodeficient xenograft models and tumor cell lines.

[figure not shown]
**Figure 6.2.** Immunoassays to measure the PD effects of checkpoint blockade agents can encompass effects on the immune cell-tumor cell interface, the T cell, and adjoining tumor cells (adapted from Parchment *et al* [68]).

The Pharmaceutical Assay Development and Implementation Lab (PADIS) at Frederick National Laboratory for Cancer Research (FNLCR) is currently developing a slide-based multiplex immunofluorescent assay to evaluate response to immune checkpoint inhibitors. Multiplexing allows geographical interpretation of tumor-immune cell interactions such that the location of TILs and T helper cells, expression of PD-L1 and PD1, and finally consequence of drug effect (e.g., apoptosis) within a tumor region of interest can be superimposed. Experimental methods using mixed cell cultures, including activated T cells, tumor cell targets, and supporting mesenchymal cells, are being used to validate measurement of PD-1 signaling in T-cells; for these assays, suitable antibodies against key signaling components have been commercially sourced, and new antibodies have been developed.

[figure not shown]
Detection of the activation of SHP-1, SHP-2, CD3zeta, and ZAP70, as well as the presence of PD1, PDL1, Ki67, and T cell phenotyping markers, has been validated in these systems and in TMAs. The following biomarkers can be imaged in formalin-fixed paraffin embedded sections (Figures 7.2-12); multiplex image capture and image analysis algorithms to quantify the biomarker staining are in development:

[figure not shown]
**Figure 7.2.** Two-plex IF. PD-L1 and CD45 common leukocyte antigen in a TMA of NSCLC cases.

[figure not shown]
**Figure 8.** IHC and IFA analyses of PD-1 in FFPE sections of pelleted CD3/CD28-stimulated human T cells *in vitro*.

[figure not shown]
**Figure 9.** Two-plex IFA of CD8 (CTL)-restricted analysis of PD-1 signaling via pY580SHP2 in CD3/28/137-stimulated human T cells *in vitro*.

**Figure 10.** IHC analysis of pY580SHP2 in FFPE sections of pelleted CD3/28/137-stimulated human T cells *in vitro*.

**Figure 11.** IHC analysis of pY493ZAP70 in FFPE sections of pelleted CD3/28/137-stimulated human T cells *in vitro*. The antibody to Zap70-pY493 is specific for pY493 epitope, as it can be blocked by incubation with the Zap70-pY493 peptide and not with the Zap70-pY492 peptide.

**Figure 12.** Zap70-pY493 staining of RDP 0707 CD3 cells stimulated with anti-CD3, CD28 and CD137 beads. Co-staining with CD8 is also shown. Zap70-pY493 signal will be thresholded based on positive and negative T cell controls and patient data can be reported as % CD8 with net positive or negative phospho-Zap70 pY493 signal.

**Samples for correlative studies will be collected from the triplet cohorts only.**

Paired biopsies (optional during the doublets and triplet escalation phase, mandatory during the triplet expansion phase) will be collected pretreatment and once at the end of cycle 1 (between days 40-42). Biopsy samples will be analyzed for:

- Status of PD1/PD-L1 checkpoint signaling
  - PD-1, PD-L1, PD-L2 (IHC)
  - pPD-1, phosphorylated cytoplasmic tail (qIFA)
    - For evidence of disruption of PD-L1 binding
  - pYSHP1, and possibly pYSHP2/ pYSHP2
- Tumor content of Tregs, CTLs, and myeloid-derived suppressor cells (MDSCs)
  - CD8, CD4, and Ki67 expression
  - CD69, TIM-1 and LAG-3
    - For immune cell activation
- Status of TCR activation
  - Activated T-cell receptor (TCR), specifically phosphorylated Zeta chain (p $\zeta$  TCR) (qIFA)
    - For evidence of tumor immunity; TCR recognition of tumor antigen/T cell activation is a prerequisite for obtaining clinical benefit with immune checkpoint blockade
  - Activated ZAP70 (phosphorylated ZAP70-pY493) (qIFA)
    - For net balance between stimulatory and inhibitory signals
- Activation of intrinsic apoptosis signaling, using a validated, clinically suitable multiplexed immunoassay [69]
- Endothelial CAM expression
- JAK/STAT pathway analysis to further assess immune signaling: Nuclear phosphoSTAT3 and phosphoSTAT5 levels

Priority will be given to assays analyzing the status of PD1/PD-L1 checkpoint signaling and T cell activation, specifically Zap70-pY493. As Zap70 is the integration point between stimulatory (TCR) and inhibitory (immune checkpoint) signaling, phosphorylation on Y493 indicates that, as a result of immune checkpoint blockade, the net signaling has resulted in a T cell response. The other proposed assays will be performed if sufficient tissue is available.

Blood samples (optional during the doublets, mandatory during the triplet escalation/expansion phases) will also be collected throughout the triplet study (See [Section 9.3](#)) and will be analyzed for:

- Activation status of peripheral T cell subsets based on intracellular phosphomarkers (TCAP1) by flow cytometry
- Investigation of the expansion of NK cells and Gamma Delta-T cells (TCAP1-NK) by flow cytometry

T cell activation panel 1 (TCAP1) is a phospho-flow assay and the TCAP1-NK assay panel is a similar flow cytometric assay validated at PADIS using healthy donor PBMCs. Similarly to the IFA assay for biopsies discussed above, the TCAP1 assay allows the measurement of phosphorylation status of proteins related to T cell activation on circulating CD4+ and CD8+ T cells. The TCAP1-NK assay detects NK cells and Gamma Delta-T ( $\gamma\delta$ ) cells and these immune cells are being investigated further to assess IL-15 impact on NK cells given that the Thomas Waldmann phase 1 trial with IL-15 (administered by continuous intravenous infusion) showed an IL-15-mediated expansion of NK-cell subsets [70]. The full TCAP1 and TCAP1-NK staining panel can be seen in Table 4 below.

**Table 4. TCAP1 and TCAP1-NK Flow panel**

	Target	Fluorochrome
Gating	CD3	PE-Cy7
	CD4	BV421
	CD8	BB700
	CD45	PE-CF594
	CD33	BV786
Analysis	CD279 (PD-1)	BV650
	Lck (pTyr505)	BV605
	Zap70 (pTyr493)	AF647
	SHP-2 (pTyr542)	PE
	CD3z (pTyr142)	AF488
	CD274 (PD-L1)	BV711
	CD56 (TCAP1-NK)	NCAM16.2
	CD16 (TCAP1-NK)	3G8
	TCR $\gamma\delta$ 1 (TCAP1-NK)	TS8.2
	TCR $\gamma\delta$ 2 (TCAP1-NK)	B6

### 2.3.1 Exploratory Laboratory Analyses

Exploratory genomic analysis may be performed on tumor biopsy samples from patients that respond to treatment. At the PI's discretion, patients on the triplet escalation/expansion phases that have baseline biopsy samples available (archival or collected on study) may be asked to undergo an additional optional biopsy at the time of confirmed response (patients that have already given two biopsies on study would not be eligible for this optional time-of-response biopsy, as the maximum number of biopsies per patient on this study is two). These biopsy samples will be used for whole exome (WES) and whole transcriptome (RNASeq) genomic analysis to enable the assessment of genomic alterations and gene expression changes associated with response (additional assays may be performed at the PI's discretion if an adequate amount of tumor tissue is collected). These data will be compared to data from germline blood to identify somatic variants. Comparison of the baseline sample to the post-treatment sample would reveal genomic changes that occur in the tumor with treatment over time and potentially shed light on the mechanisms of response to rhIL-15, ipilimumab, and nivolumab combination therapy. Genes of interest would include those involved in the immune response and antigen presentation (JAK/STAT pathway, TGF $\beta$  pathway, HLA genes) [71]. WES data would also be

used to determine tumor mutational burden (TMB), a biomarker previously shown to be associated with better survival after checkpoint inhibitor therapy [72, 73]. These exploratory sequencing results would not be shared with patients.

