### 1.2 Exploratory Objectives

**1.2.1** Assess the clinical activity of rhIL-15, ipilimumab, and nivolumab combination therapy as characterized by RECIST 1.1 and immune RECIST (iRECIST) response rate of patients treated in this trial

**1.2.2** Investigate the biological effects of this combination on circulating T cell subsets and on PD-1/PD-L1 expression and immune cell activation in tumor biopsies

**1.2.3** Perform genomic analysis on tumor biopsies in order to identify genomic alterations and gene expression changes associated with clinical response to rhIL-15, ipilimumab, and nivolumab combination therapy

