**9.1.2 Genomic Analysis**

At the PI's discretion, patients on the triplet escalation/expansion phases **that have baseline biopsy samples available** (archival or collected on study) may be asked to undergo an additional optional biopsy at the time of confirmed response. If the biopsy is successful, exploratory WES and RNASeq will be performed on both the baseline biopsy sample and the time-of-response biopsy sample, enabling the assessment of genomic alterations that 1) occur with treatment over time and 2) possibly correlate with response (see [Section 2.3: Exploratory Laboratory Analyses](#)). Genes of interest would include those involved in the immune response and antigen presentation (JAK/STAT pathway, TGF $\beta$  pathway, HLA genes). Data from germline sequencing will be used to determine which tumor mutations are somatic variants (see [Section 9.3.2](#)).

Patients that have already given two biopsies on study (at the protocol-specified timepoints, baseline and C1D42) **would not be eligible** for this optional time-of-response biopsy, as the maximum number of biopsies per patient on this study is two.

Additional genomic assays may be performed on leftover tissue/genomic material from the baseline biopsy sample and the time-of-response biopsy sample at the PI's discretion.

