### **9.2.1 Solid Tumor Biopsy Processing**

Five tissue cores, or equivalent, will be obtained at each time point. Each biopsy sample will be transferred into a 1.5-mL pre-chilled cryovial and then flash frozen in liquid nitrogen per DCTD SOP340507

([http://dctd.cancer.gov/ResearchResources/biomarkers/docs/par/SOP340507\\_Biopsy\\_Frozen.pdf](http://dctd.cancer.gov/ResearchResources/biomarkers/docs/par/SOP340507_Biopsy_Frozen.pdf)). Biopsies should be placed in cryogenic vials and frozen within 2 minutes of collection. Three biopsy samples will be used for pharmacodynamic assays to measure immune checkpoint targets and the anti-tumor immune response as described above, and the other two will be used for genomic analysis if appropriate. Remaining samples will be kept in the Frederick National Laboratories CR Biorepository in liquid nitrogen freezers to be used for validation of these assays as necessary.

Shipment should be by CSP Courier and may be arranged by contacting [name], FNLCR, [contact]. The Clinical Center should notify [NCI\\_PD\\[contact]](mailto:[contact]) with sample information.

Flash-frozen biopsy cores for PD analysis will be shipped on dry ice to:

Attn: PADIS IQC Lab  
Frederick National Laboratory for Cancer Research  
Leidos Biomedical Research, Inc.  
[name]  
[name]  
[name]  
[contact]  
[NCI\\_PD\\[contact]](mailto:[contact])

Please contact [name] (office: [contact], [contact]) or [name] (office: [contact], [contact]) (email: [NCI\\_PD\\[contact]](mailto:[contact])) to ask any questions regarding storage or shipment of these specimens.

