### **9.2.2 Archival Tissue Submission**

Archival tumor tissue submitted as a baseline specimen for PD studies must have been collected within 3 months prior to patient registration, and the patient must not have received any intervening cancer therapy since collection of the specimen. Archival tissue must have been collected and processed according to NCI DCTD SOP340507 ([https://dctd.cancer.gov/ResearchResources/biomarkers/docs/par/SOP340507\\_Biopsy\\_Frozen.pdf](https://dctd.cancer.gov/ResearchResources/biomarkers/docs/par/SOP340507_Biopsy_Frozen.pdf)), including flash-freezing in liquid nitrogen, minimal cold ischemia time (< 5 minutes), and shipment on dry ice. Formalin-fixed biopsy tissue is not compatible with the immunoPD assay.

These restrictions do not apply for the use of archival tissue for genomic studies. Use of archival tissue as a baseline genomic sample will be at the discretion of the PI and the Molecular Characterization Laboratory (MoCha) at Frederick National Laboratory for Cancer Research (FNLCR).

Please send an email to FNLCR PD Specimen Central Receiving (NCI\_PD\[contact]) to advise that archival tissue is being prepared for shipment. State “Protocol Name PD Specimens Ready for Shipment” in the subject line. If needed, FNLCR PD Central Receiving can be contacted directly at [contact] or [contact].

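### With no non-responders sequenced, the genomic plan can describe change within a few responders but cannot identify alterations associated with response, as objective 1.2.3 is worded.

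*Combined protocol and SAP*

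**What the plan says.** Objective 1.2.3 reads: "Perform genomic analysis on tumor biopsies in order to identify genomic alterations and gene expression changes associated with clinical response" to the triple combination. Section 2.3.2 supports that reading, since it wants response data so that sequencing results can be compared with them.

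The operational text is narrower:

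- **Who is analysed.** Section 2.3.1: "Exploratory genomic analysis may be performed on tumor biopsy samples from patients that respond to treatment". Selection is at the PI's discretion, among triplet patients who have a baseline sample.
- **What triggers sequencing.** Section 9.1.2: "If the biopsy is successful, exploratory WES and RNASeq will be performed on both the baseline biopsy sample and the time-of-response biopsy sample". The baseline sample therefore waits on the later biopsy.
- **Who is ineligible for that biopsy.** Section 2.3.1: "patients that have already given two biopsies on study would not be eligible for this optional time-of-response biopsy". Section 9.1.2 gives the reason: "as the maximum number of biopsies per patient on this study is two". Sections 5 and 9.1.1 make the baseline and cycle 1 day 42 (C1D42) biopsies mandatory in the expansion cohort.
- **Germline blood.** Section 9.3.2 and footnote m of the triplet calendar (10.2) collect it only from responders who agree to the extra biopsy.
- **Cores set aside.** Section 9.2.1 assigns three of the five cores at each time point to pharmacodynamic (PD) assays, and "the other two will be used for genomic analysis if appropriate".
- **Archival baselines.** Section 9.2.2 requires archival tissue for PD work to be recent and free of intervening cancer therapy. It then adds: "These restrictions do not apply for the use of archival tissue for genomic studies".

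**The concern.** Association with response is a contrast between patients who respond and patients who do not. If only responders are sequenced, a mutation, an expression shift or a level of tumour mutational burden may be frequent among them because of the treatment, the passage of time, the tumour type, or because it is frequent in everyone. Nothing in the data separates these explanations. Section 2.3.1 also plans to derive tumour mutational burden, a between-patient marker that responder-only data cannot relate to response.

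Two features add to this. The biopsy cap falls hardest on the cohort where tissue collection is mandatory. And because archival genomic baselines may predate other therapy, while criterion 3.1.11 admits patients who progressed on a study agent or another checkpoint inhibitor, a baseline-to-response difference may include the effect of earlier treatment. Section 2.3.1 would read it as change occurring with study treatment.

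At stake is what an exploratory report may claim. Dose escalation and safety decisions are unaffected.

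**Working it through.** **1. Is there a planned figure to reproduce?** Not for genomics: no sample size, power or expected yield is given. The nearest figures concern usable PD pairs (sections 5.1.2.2 and 13.1): 15 patients, 50% failure. P(X ≥ 6 | 15, 0.5) = 0.849 against the stated 85%, and P(X ≥ 5) = 0.941 against the stated 95%. Both agree to within about a point, but they describe paired PD biopsies, not sequencing.

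**2. Comparison group.** Sections 2.3.1, 9.1.2, 9.3.2 and 10.2 all point to the same patients: responders with a baseline sample and a successful time-of-response biopsy. Planned non-responders sequenced = 0, whatever the response rate.

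**3. Effect of the cap in expansion.** Restaging is every 6 weeks ± 1 week, so a confirmed response will normally come after C1D42. A compliant expansion patient with a fresh baseline biopsy has by then given two biopsies and cannot have a third. The exceptions are narrow:

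- An archival PD baseline leaves one biopsy unused, but must meet the section 9.2.2 conditions.
- A patient who declines C1D42 stays on study, but section 9.2 says that no more biopsies follow a refusal. Read literally, that closes the response biopsy too.

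**4. How many responders?** The response rate is an assumption, shown over 10 to 30%. The only nearby figure, 15 to 20% in section 2.1, is for single-agent anti-PD-1 in lung cancer. With all three dose levels opened, escalation has 3 × 3 = 9 to 3 × 6 = 18 patients (section 5.1.2) and expansion has 15. Expected responders = n × p; chance of none = (1 − p)^n.

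| Group | n | p = 10% | 15% | 20% | 30% |
|---|---|---|---|---|---|
| Escalation, smallest | 9 | 0.9 (0.387) | 1.35 (0.232) | 1.8 (0.134) | 2.7 (0.040) |
| Escalation, largest | 18 | 1.8 (0.150) | 2.7 (0.054) | 3.6 (0.018) | 5.4 (0.002) |
| Expansion | 15 | 1.5 (0.206) | 2.25 (0.087) | 3.0 (0.035) | 4.5 (0.005) |

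Entries are expected responders (chance of none). They are upper limits on pairs, before allowing for consent, the restriction to patients enrolled after Amendment G (section 2.3.2), missing baseline tissue and biopsy failure. Most expansion responders drop out under step 3.

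**5. Would sequencing only expansion pairs supply the contrast?** Borrowing the 50% PD failure rate as an assumption, 15 × 0.5 = 7.5 pairs. At 10 to 20% response these hold 0.75 to 1.5 responders. The chance of no responder runs from 0.8^8 = 0.17 to 0.9^7 = 0.48. With one responder against 6 or 7 non-responders, the smallest two-sided Fisher p-value is 1/7 = 0.14 or 1/8 = 0.125, so even perfect separation would not reach 0.05.

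**6. Would sequencing all triplet baselines?** If all 18 + 15 = 33 patients gave usable samples and 15 to 20% responded, the split would be about 5 v 28 to 7 v 26. Fisher power (two-sided 0.05) is 37 to 47% for an alteration present in 60% v 20%, and 73 to 82% for 80% v 20%. The standardised difference detectable with 80% power in a continuous marker is 1.4 to 1.2 SD. The contrast becomes estimable, but only for large effects.

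**The case against.** The best defence is that the plan's own text supports a narrower aim. Section 2.3.1 describes comparing each responder's baseline with the later sample to learn about mechanisms of response, and section 9.1.2 speaks only of possible correlation. The work is optional, section 13.3 promises caveats, and no power is claimed. That stands in part: responder-only pairs can serve a within-patient description. It does not rescue objective 1.2.3, because caveats about exploratory status do not supply a missing comparison group.

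A reader might infer that expansion patients with two biopsies are shut out of genomic work altogether. The documents do not say so. The cap applies to the time-of-response biopsy, and section 9.2.1 reserves cores for genomics at each time point. What is missing is a stated use for the C1D42 cores and a germline sample to go with them. Those cores are not guaranteed either: section 9.2 sets five as an upper limit, and section 9.1.1 gives priority to certain PD assays.

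On archival tissue, section 9.2.2 leaves its use as a genomic baseline to the PI and the molecular laboratory. That is some control over selection, but not a rule for reporting.

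**Conclusion.** The concern holds as a mismatch between objective and plan. No non-responder is scheduled for sequencing, so association with response cannot be estimated at any response rate. This conclusion rests on the text alone. The yield of within-patient pairs is small: at an assumed 15 to 20% response, about 1.4 to 3.6 escalation responders before further losses, plus the few expansion responders who have not used both biopsies.

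It would be too strong to say that the genomic work has no value or that the objective is beyond reach. Within-patient change in a few responders can be described, and the association aim could be restored by widening who is sequenced. Nor do the calculations support the idea that sequencing expansion pairs alone would repair it, since the responder group would nearly vanish. The primary objective is untouched.

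**What to change.** Three changes to the text, none needing another biopsy:

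1. Restate objective 1.2.3, and the matching text in sections 2.3.1, 2.3.2 and 9.1.2, as a descriptive account of within-patient changes in responders, with no claim of association with response.
2. Reconcile section 9.2.1 with sections 9.1.2 and 9.3.2: say whether the reserved baseline and C1D42 cores are sequenced, for whom, and with what germline sample.
3. Report changes measured from archival baselines with intervening therapy separately, and do not attribute them to study treatment.

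Items 1 and 3 cost only wording and a reporting rule. Item 2 costs wording, plus sequencing if the answer is yes.

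Optional, if the sponsor wants to keep the association objective: sequence baseline tumour and germline blood from all consenting triplet patients with tissue, in escalation and expansion alike and whatever their response. Report the responder v non-responder contrast as hypothesis-generating. This adds sequencing cost, two 10-mL germline tubes per patient (section 9.3.2), and wider duties under section 9.5 to confirm and return actionable germline findings. It remains subject to the optional genetic consent in section 2.3.2. Any yield based on the 50% failure rate should be marked as an assumption, because section 13.1 gives that rate for PD pairs.

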### 2.3.2 Genetic Sequencing Research Ethics

This trial may collect identifiable genetic data from patients enrolled after **Amendment G** (3/4/20) for exploratory studies to examine genomic alterations and gene expression patterns potentially associated with sensitivity to treatment. As patient clinical response data will be required for comparison to sequencing results, de-identifying the samples is not feasible. Designing the study therefore poses challenging questions about informed consent, the privacy of the patient and the patient's family, the researchers' obligation to disclose genetic information to the patient, and the use and storage of research data [74-76]. In the vast majority of cases, we do not know the medical significance of genetic variants [77, 78]. These challenges will continue to be evaluated to maintain the rigor and integrity of the study and the well-being of our patients. A Certificate of Confidentiality has been obtained from the NIH to help protect the privacy of all study participants.

The informed consent document for this protocol after **Amendment G** (3/4/20) contains language informing patients about the performance of genetic studies, and patients will have the option to choose whether they wish to take part in these studies.

Whole-exome sequencing (performed for research purposes; non-CLIA) of tumor and blood can detect non-ambiguous germline variants, which may raise health and privacy implications for the patient and his or her family. WES will not be validated for clinical use, and no clinical decisions can be made based on its results (see [Section 9.5](#)).

This study does not meet the criteria specified by the NIH Genomic Data Sharing (GDS) Policy and therefore a GDS plan has not been included in this protocol.

